9.4 PLANNED ANALYSES

Survival data will be analyzed using parametric (exponential) and non-parametric (Kaplan-Meier) methods. Exact methods for providing confidence intervals for proportions “surviving” landmarks will be used as needed. Statistical software will be SAS (and others as merited) and analysis will be conducted under the supervision of [name], in the Biostatistical Core Facility at Northwestern University.

Descriptive statistics (mean, standard deviation, mean change from baseline, etc.) will be presented for laboratory values. Detailed examination of AEs by NCI CTCAE grade and frequency tabulation will be presented. Missing data for partial dates on AEs or concomitant medications may be imputed.

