9.3 TRIAL DESIGN AND DETERMINATION OF SAMPLE SIZE

A two-stage optimal Simon design will be employed to test the null hypothesis that the probability of progression-free survival of 4 months or greater (P) is ≤ 0.22 versus the alternative that the probability ≥ 0.45 . To test this hypothesis with adequate power, a first stage involving 12 patients will be completed. If > 3 patients achieve progression-free survival of 4 months, the trial will be continued for a total of 31 patients. If > 11 out of 31 patients achieve progression-free survival of 4 months, the trial will reject the hypothesis that $P \leq 0.22$ and conclude that $P > 0.45$,

To determine sample size, the following parameters were employed: $P0 = 0.22$, $P1 = 0.45$, $\alpha = 0.05$ and $\beta = 0.20$. Computations originally performed using software PASS (www.ncss.com).

N1	R1	PET	N	R	Avg N	α	β	Satisfied
26	9	0.000	26	9	26.00	0.043	0.194	Single Stage
7	0	0.176	26	9	22.66	0.042	0.199	Minimax
12	3	0.739	31	10	16.96	0.047	0.188	Optimum

Definitions:

N1 – sample size in the first stage

R1 – drug rejection number in the first stage

PET – probability of early termination of study

N – combined sample size of both stages

R – combined drug rejection number after both stages

Avg N – average sample size if this design is repeated many times

α – probability of rejecting that $P < P0$ when this is true

β – probability of rejecting that $P > P1$ when this is true

P0 – response proportion P of a poor drug

P1 – response proportion P of a good drug

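### Section 9.4 sets no two-stage interval or confidence level for the 4-month rate, so a fixed-sample exact interval could contradict the primary test at the boundary count

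*Combined protocol and SAP*

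**What the plan says.** Section 9.3 fixes the test: "A two-stage optimal Simon design will be employed", with a null rate of 0.22, an alternative of 0.45, alpha 0.05 and beta 0.20. The hypotheses are directional, so the test is one-sided in use. For stage 1, "a first stage involving 12 patients will be completed"; with more than 3 successes, "the trial will be continued for a total of 31 patients".

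The final rule is given twice, and the two versions differ. The text requires more than 11 successes: "out of 31 patients achieve progression-free survival of 4 months, the trial will reject the hypothesis". The table row for the chosen design reads "12 3 0.739 31 10 16.96 0.047 0.188 Optimum". Its R = 10 means rejection at 11 or more.

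Section 9.4 is the whole estimation plan. Beyond exponential and Kaplan-Meier analyses, it offers "Exact methods for providing confidence intervals for proportions" at landmarks, as needed. It names no interval method, no confidence level, no estimator for the 4-month rate and no adjustment for the interim stop. Section 6.3 defines a count over the total, but only for the 3- and 6-month rates.

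**The concern.** A fixed-sample exact interval treats the 31 patients as if all had been certain to be enrolled. Under the design, a trial with 3 or fewer successes among the first 12 never reaches 31. The test takes account of this; a Clopper-Pearson interval does not. The interval and the test therefore answer to different sampling distributions, and near the rejection threshold they can disagree.

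At stake is the reported result. The trial could declare that the rate exceeds 0.22 and print beside that an interval containing 0.22. With method and level both unspecified, the choice could also be made after the count is known. Appendix VI (Amendment 1) describes the 4-month rate as the only endpoint designed with a pre-identified error risk, so its interval is the one that should be fixed in advance.

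**Working it through.** **Inputs** (Section 9.3): n1 = 12, r1 = 3, N = 31 (so n2 = 19), P0 = 0.22, P1 = 0.45; final rule R = 10 (table) or more than 11 (text). The confidence level is not in the documents. I show two-sided 90%, which matches a one-sided 5% test, and two-sided 95%. All 31 patients are assumed to count in the denominator.

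**1. Reproduce the plan's figures.**
- Early termination: P(X1 ≤ 3; 12, 0.22) = 0.0507 + 0.1717 + 0.2663 + 0.2503 = 0.739.
- Average N: 12 + 19 × (1 − 0.739) = 16.96.
- P(reject) = Σ over x1 = 4 to 12 of b(x1; 12, p) × P(X2 ≥ R + 1 − x1; 19, p). With R = 10 this is 0.0468 at p = 0.22 and 0.8117 at p = 0.45 (beta 0.188). All agree with the table.
- The text rule (more than 11) gives instead alpha 0.0221 and power 0.752.

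**2. Compare the p-values at 11/31.** The two-stage p is the sum above, 0.0468. The fixed-sample p is P(X ≥ 11; 31, 0.22) = 0.0607. The difference, 0.0139, is the probability of sequences with 11 or more successes in 31 but 3 or fewer in the first 12. The stopping rule makes these impossible.

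**3. Compare the intervals.** Fixed-sample limits are Clopper-Pearson. Two-stage limits invert the tail probabilities of the two-stage distribution, ordering outcomes by stage and then by count. Ordering by the uniformly minimum variance unbiased estimator (UMVUE) gives the same order here.

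| Count | Level | Fixed-sample | Two-stage |
|---|---|---|---|
| 11/31 | 90% | 0.213–0.518 (contains 0.22) | 0.222–0.550 (excludes) |
| 11/31 | 95% | 0.192–0.546 (contains) | 0.200–0.586 (contains) |
| 12/31 | 90% | 0.241–0.550 (excludes) | 0.247–0.569 (excludes) |
| 12/31 | 95% | 0.2185–0.578 (contains) | 0.224–0.601 (excludes) |
| 13/31 | 95% | 0.2455–0.609 (excludes) | 0.249–0.621 (excludes) |

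**4. How often.** At p = 0.45 the chance of exactly 11/31 is 0.0597 and of exactly 12/31 is 0.0915.
- Table rule, 90% fixed-sample interval: conflict at 11/31 only, 0.0597/0.8117 = 7% of rejections.
- Table rule, 95%: conflict at 11/31 and 12/31, (0.0597 + 0.0915)/0.8117 = 19%. The 11/31 part remains after adjustment, because there a two-sided 95% interval sits beside a one-sided 5% test.
- Text rule, 95%: 0.0915/0.7519 = 12%. Text rule, 90%: none.

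**5. Point estimate.** The UMVUE is Σ C(11, x1 − 1)C(19, s − x1) / Σ C(12, x1)C(19, s − x1), summed over x1 ≥ 4. It gives 0.408 at 11/31 (observed 0.355) and 0.426 at 12/31 (observed 0.387).

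Averaged over both stages, the observed proportion is low by 0.025 at p = 0.22, 0.033 at 0.30 and 0.019 at 0.45. Given continuation to stage 2, it is high by 0.061 at 0.22 and 0.014 at 0.45. Given rejection at 0.45, it is high by 0.025 (table rule) or 0.034 (text rule), and the UMVUE is high by about 0.043 or 0.049.

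**The case against.** The plan does not prescribe a wrong method. A two-stage exact interval is also an exact method, and Section 9.4 names neither Clopper-Pearson nor the observed proportion for the 4-month rate. A reader might infer that the plan commits itself to ignoring the design; the text supports only that no design-based method is specified. This stands.

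The decision is a count against a threshold derived from the two-stage distribution, so no interval can change it. This stands.

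The conflict is narrow. It arises only at boundary counts and depends on the level: at 12/31 the 95% lower limit misses 0.22 by 0.0015, a 90% interval shows no conflict, and from 13/31 upwards even the fixed-sample 95% interval excludes 0.22. This stands too, but at 11/31 under the table rule the conflict occurs at the very level that matches the test, and only the neglect of the design explains it.

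Coverage is not seriously at fault. The fixed-sample 95% interval covers at or above nominal for most rates and falls slightly short only around 0.5 to 0.6, to about 0.94 near 0.58. The main defect is inconsistency with the test.

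Making the UMVUE the primary estimate would be a trade-off. Its root mean squared error is larger at p = 0.22 (0.116 against 0.093) and 0.30 (0.121 against 0.108), and only slightly smaller at 0.45 (0.111 against 0.117). That argues for keeping it as a supplement.

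**Conclusion.** The point holds as a gap in the reporting plan. Section 9.4 sets no level and makes no allowance for the stage-1 stop, and the customary reading of an exact interval can contradict the primary test at one boundary count: 11/31 at 90% under the table rule, or 12/31 at 95% under the text rule. At a true rate of 0.45 these are 7% and 12% of rejections respectively. The size rests on two assumptions: that Clopper-Pearson would be used, and which level would be chosen.

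A reader might also infer that the estimate passed on to later trials would be understated. The documents do not support that. Section 1.2 ties later trials to this one meeting its efficacy criteria, and among trials that continue or reject, the observed proportion is high on average. The low bias of 0.02 to 0.03 appears only when trials stopped at 12 patients are averaged in.

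**What to change.** First reconcile the rule of more than 11 in the text of Section 9.3 with R = 10 in its table, because this determines which count is the boundary.

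Then add a sentence to Section 9.4: the 4-month rate will be reported as the observed proportion, with a p-value and a two-sided 90% confidence interval computed from the two-stage sampling distribution (Jung-Kim or Koyama-Chen), consistent with the one-sided 5% test; the UMVUE may be shown as a supplement.

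The 90% level agrees with the table rule. If the text rule is kept, a two-stage 90% interval would exclude 0.22 at 11/31 without a rejection. The attained alpha of 0.022 would then pair with a two-sided 95% interval, so the level should be confirmed once the rule is settled.

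The cost is one sentence and a few lines of code, with no further data or patients. The downside is a wider interval with a higher upper limit: at 11/31 the 90% width rises from 0.305 to 0.328.

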10.0 STUDY MANAGEMENT

10.1 INSTITUTIONAL REVIEW BOARD (IRB) APPROVAL AND CONSENT

It is expected that the IRB will have the proper representation and function in accordance with federally mandated regulations. The IRB should approve the consent form and protocol.

In obtaining and documenting informed consent, the investigator should comply with the applicable regulatory requirement(s), and should adhere to Good Clinical Practice (GCP) and to ethical principles that have their origin in the Declaration of Helsinki. Before recruitment and enrollment onto this study, the patient will be given a full explanation of the study and will be given the opportunity to review the consent form. Each consent form must include all the relevant elements currently required by the FDA Regulations and local or state regulations. Once this essential information has been provided to the patient and the investigator is assured that the patient understands the implications of participating in the study, the patient will be asked to give consent to participate in the study by signing an IRB approved consent form.

Prior to a patient’s participation in the trial, the written informed consent form should be signed and personally dated by the patient and by the person who conducted the informed consent discussion.

10.2 AMENDMENTS

The Principal Investigator will formally initiate all amendments to the protocol and/or informed consent. Modifications to the study protocol will not be implemented by the investigator without discussion and agreement by Bayer. All amendments will be subject to the review and approval of the appropriate local, institutional, and governmental regulatory bodies. Amendments will be distributed by the lead institution (Northwestern) to all affiliate sites upon approval by the Northwestern University IRB.

10.3 REQUIRED DOCUMENTATION FOR MULTI-SITE STUDIES

Before the study can be initiated at any site, the following documentation must be provided to the Clinical Research Office at Northwestern University:

- 10.3.1** Signed and completed Letter of Invitation to participate in the study.
- 10.3.2** Signed copy of Northwestern University's Data Monitoring Committee policy pertaining to data submission.
- 10.3.3** A copy of the official IRB approval letter for the protocol and informed consent.

NOTE: Informed consent form should be submitted to the Clinical Research Office for review/approval prior to submission to the local IRB.

- 10.3.4** CVs and medical licensure for the principal investigator and any associate investigators who will be involved in the study at the site.
- 10.3.5** Form FDA 1572 appropriately filled out and signed with appropriate documentation.

Additional activities may be required prior to site activation (i.e. contract execution, study-specific training). Full requirements will be outlined in a memo upon receipt of the signed Letter of Invitation.

10.4 SUBJECT REGISTRATION PROCEDURES

Patients may not begin protocol treatment prior to registration. All patient registrations will be registered centrally through the Clinical Research Office at Northwestern University before enrollment to study. Please contact the assigned Quality Assurance Monitor (QAM) or email the QA Department ([contact]) for questions regarding patient registration.

Prior to registration, eligibility criteria must be confirmed by the assigned QAM. The study coordinator will screen all subjects for potential registration via the web-based application NOTIS (Northwestern Oncology Trial Information System), which is available at: <https://notis.nubic.northwestern.edu>. Please note that a username and password is required to use this program, and will be provided during site activation prior to training on the NOTIS system.

Registering a Patient to a Phase II Study

For potential patients this study, study teams are asked to inform the QAM of the date and time that the patient will need to be registered ([contact]).

BEFORE a patient can be treated on study, please complete and submit the following items to confirm eligibility and receive a subject identification number:

- Eligibility eCRF (complete in NOTIS)
- Eligibility checklist (signed and dated by the treating physician – upload in NOTIS)
- Signed and dated informed consent document (upload in NOTIS)

- Pathology Report (upload in NOTIS)

The QAM will review the registration, register the patient, assign a subject identification number, and send a confirmation of registration to study personnel. Registration will then be complete and the patient may begin study treatment.

10.5 DATA SUBMISSION

Once a subject is confirmed and registered to the study, eCRFs should be submitted according to the detailed data submission guidelines (provided in a separate document). Generally, for all phase II patients, data are due at the end of every cycle within 10 days.

10.6 DATA MANAGEMENT AND MONITORING/AUDITING

This study will be conducted in compliance with the Data Safety Monitoring Plan (DSMP) of the Robert H. Lurie Comprehensive Cancer Center of Northwestern University (please refer to NOTIS for additional information). The level of risk attributed to this study requires High Intensity Monitoring, as outlined in the DSMP. The assigned QAM, with oversight from the Data Monitoring Committee, will monitor this study in accordance with the study phase and risk level. Please refer NOTIS for additional data submission instructions.

10.7 ADHERENCE TO THE PROTOCOL

Except for an emergency situation in which proper care for the protection, safety, and well-being of the study patient requires alternative treatment, the study shall be conducted exactly as described in the approved protocol.

10.7.1 Emergency Modifications

Investigators may implement a deviation from, or a change of, the protocol to eliminate an immediate hazard(s) to trial subjects without prior IRB approval.

For any such emergency modification implemented, an IRB modification form must be completed within five (5) business days of making the change.

10.7.2 Other Protocol Deviations

All other deviations from the protocol must be reported to the assigned QAM using the appropriate form.

A protocol deviation is any unplanned variance from an IRB approved protocol that:

- 10.6.2.1 Is generally noted or recognized after it occurs.

- 10.6.2.2 Has no substantive effect on the risks to research participants
- 10.6.2.3 Has no substantive effect on the scientific integrity of the research plan or the value of the data collected.
- 10.6.2.4 Did not result from willful or knowing misconduct on the part Of the investigator(s).

A protocol deviation may be considered an instance of Reportable New Information (RNI) if the variance:

- 10.6.2.5 Has harmed or increased the risk of harm to one or more research participants.
- 10.6.2.6 Has damaged the scientific integrity of the data collected for the study.
- 10.6.2.7 Results from willful or knowing misconduct on the part of the investigator(s).
- 10.6.2.8 Demonstrates serious or continuing noncompliance with federal regulations, State laws, or University policies.

10.8 OBLIGATIONS OF INVESTIGATORS

The Principal Investigator is responsible for the conduct of the clinical trial at the site in accordance with Title 21 of the Code of Federal Regulations and/or the Declaration of Helsinki. The PI is responsible for personally overseeing the treatment of all study patients. The PI must assure that all study site personnel, including sub-investigators and other study staff members, adhere to the study protocol and all FDA/GCP/NCI regulations and guidelines regarding clinical trials both during and after study completion.

The Principal Investigator at each institution or site (local PI) will be responsible for assuring that all the required data will be collected, entered onto the appropriate eCRFs, and submitted within the study-specific timeframes. Periodically, monitoring visits may be conducted and the Principal Investigator will provide access to his/her original records to permit verification of proper entry of data. The study may also be subject to routine audits by the Audit Committee, as outlined in the DSMP.

10.9 PREMATURE TERMINATION OF THE STUDY

The study may be halted prematurely for any of the following reasons:

- If risk-benefit ratio becomes unacceptable owing to, for example:
 - Safety findings from this study (e.g. SAEs)
 - Results of any interim analysis
 - Results of parallel clinical studies
 - Results of parallel animal studies (on e.g. toxicity, teratogenicity, carcinogenicity or reproduction toxicity).
- If the study conduct (e.g. recruitment rate; drop-out rate; data quality; protocol compliance) does not suggest a proper completion of the trial within a reasonable time frame.

For any of the above closures, the following applies:

- Closures should occur only after consultation between involved parties (including approval from the Data Monitoring Committee at Northwestern University).
- All affected institutions and their IRBs, competent authority (ies), study center, and the head of study center must be informed as applicable according to local law.

- In case of a partial study closure, ongoing subjects, including those in post study follow-up, must be taken care of in an ethical manner.

10.10 PUBLICATION POLICY

All potential publications and/or data for potential publications (e.g. manuscripts, abstracts, posters, clinicaltrials.gov releases) must be approved in accordance with the policies and processes set forth in the Lurie Cancer Center DSMP. For trials that require high intensity monitoring, the assigned QAM will prepare a preliminary data summary (to be approved by the DMC) no later than 3 months after the study reaches its primary completion date (the date that the final subject is examined or receives an intervention for the purposes of final data collection for the primary endpoint). If the investigator's wish to obtain DMC-approved data prior to this point (or prior to the point dictated by study design), the PI must send a written request for data to the QAM which includes justification. If the request is approved, data will be provided no later than 4 weeks after this request approval. The data will be presented to the DMC at their next available meeting, and a final, DMC-approved dataset will be released along with any DMC decisions regarding publication. The investigators are expected to use only DMC-approved data in future publications. The investigators should submit a copy of the manuscript to the biostatistician to confirm that the DMC-approved data are used appropriately. Once the biostatistician gives final approval, the manuscript may be submitted to Bayer Healthcare(funding source). Bayer recognizes the right of the investigator to publish results upon completion of the study. However, the investigator must send a draft manuscript of the publication or abstract to Bayer at least 30 days in advance of submission in order to obtain approval prior to submission of the final version for publication or congress presentation. This will be reviewed promptly and approval will not be withheld unreasonably. In case of a difference of opinion between Bayer and the investigator(s), the contents of the publication will be discussed in order to find a solution which satisfies both parties. All relevant aspects regarding data reporting and publication will be part of the contract between Bayer and the investigator/institution. The Principal Investigator should also ensure that the information regarding the study be publicly available on the internet at www.clinicaltrials.gov.

REFERENCES

APPENDIX III – BLOOD PRESSURE LOG

Protocol Number _____ Institution _____

Subject Initials _____ Subject ID# _____

Date of assessment	Time of assessment	Systolic/Diastolic (mmHg)	Comments
Wk1:			
Wk2:			
Wk3:			
Wk4:			
Wk5:			
Wk6:			

Blood pressure should be recorded weekly during the first six weeks of treatment.

 CRA Initials Date of Completion

APPENDIX IV – DATA SAFETY MONITORING PLAN

This trial will be conducted and monitored in accordance with the Data Safety Monitoring Plan (DSMP) of the Robert H. Lurie Comprehensive Cancer Center of Northwestern University. A copy of the plan can be obtained from the following link:

<https://www.cancertrials.northwestern.edu/cpsrms/cpsrms-p-ps>

Data is expected to be submitted according to requirements described in appendix I. The QAM will review and assess each submitted eCRF for completeness, protocol adherence/compliance, toxicities, potential subject safety issues, and disease outcome and response. The QAM will routinely query study teams regarding any issues or for outstanding data. The QAM will present SAEs, protocol deviations, data summaries, and any other issues that may impact patient safety or data integrity to the DMC on a semi-monthly basis.

APPENDIX V - ADVERSE EVENTS SELF-REPORT SURVEY

Available as stand-alone document in NOTIS

APPENDIX VI – PROTOCOL HISTORY OF CHANGES

Initial Version approved by Scientific Review Committee – May 10, 2013			
Amendment 1 (pre-IRB submission) – October 10, 2013 Approved by SRC – October 22, 2013			
Section(s) Affected	Prior Version	Amendment 1 Changes	Rationale
Throughout	n/a	Adds the Bayer Healthcare study number to the header (ONC-2013-129)	Administrative
Synopsis, 2.1 (Primary Objective), 6.2 (Primary Endpoint Assessment), 9.1 (Primary Outcome of Interest)	Primary objective was progression-free survival (PFS).	Changed primary objective to PFS at 4 months.	This was changed at the recommendation of the company providing regorafenib (Bayer Healthcare). PFS at 4 months is the only endpoint that the study is designed to assess with a pre-identified risk of error, which makes it the logical basis for conclusion of efficacy in this trial.
Synopsis, 2.2 (Secondary Objectives), 6.3 (Secondary Endpoint Assessment), 9.2 (Secondary Outcomes of Interest)	n/a	Adds overall PFS and progression-free rate (PFR) at 3 and 6 months secondary objectives.	PFR has been established as an endpoint for soft tissue sarcoma by the Soft Tissue and Bone Sarcoma Group of the European Organization for Research and Treatment of Cancer (EORTCSTBSG) to account for low PR rates in this disease. This was changed at the recommendation of Bayer Healthcare.
1.2 (Rationale)	n/a	Adds a statement that future phase III or other large-scale confirmatory trials should employ an interim analysis as an efficacy double-check if this trial meets efficacy criteria.	Added at the recommendation of Bayer Healthcare.
3.1 (Inclusion Criteria)	n/a	Adds that “Patients who are prophylactically treated with an agent such as warfarin or heparin will be allowed to participate provided	Added at the recommendation of Bayer Healthcare.

		that no prior evidence of underlying abnormality in coagulation parameters exists.” Gives recommendations for how to monitor this.	
3.1 (Inclusion Criteria)	No limit on the number of prior therapies for eligibility.	Allows up to 4 prior therapies for eligibility; clarifies that progressive disease must have been under last palliative therapy .	Added at the recommendation of Bayer Healthcare.
Table 4 (Recommended Dose Modification for Hand-Foot-Skin Reaction)	n/a	Removes footnote “e”.	Administrative – did not pertain to any part of the table.
Table 6 (Dose Modifications/Delays for Liver Function Abnormalities), Table 7 (Study Visit Parameters)	Stated that ALT, AST and bilirubin will be monitored at least weekly during the first 2 cycles of treatment.	Changes this to require monitoring prior to initiation of regorafenib treatment, and then every 2 weeks during the first 2 cycles; adds that 2 cycles = 2 months. Updates visit parameters accordingly.	Clarification and change requested by Bayer Healthcare.
4.3.5 (Prevention/Management Strategies for Diarrhea)	Stated that the same dose modification algorithm used for skin toxicities should be used for diarrhea.	Revises this to state only that diarrhea prevention and management should be consistent with local institutional practices.	Update requested by Bayer Healthcare.
4.4 (Prior and Concomitant Therapy)	General background given on the interactions of CYP3A4 inducers and inhibitors on regorafenib.	Adds detailed background information on the effects of co-administration of strong CYP3A4 inducers (such as rifampin) and strong CYP3A4 inhibitors (such as ketoconazole) on exposure of regorafenib and its metabolites.	Update requested by Bayer Healthcare.
4.4 (Prior and Concomitant Therapy)	Mentioned that “caution should be taken when considering or administering a concomitant medication that is metabolized by the cytochrome enzymes CYP2C8, CYP2B6	Removes this statement.	Per Bayer Healthcare, only strong CYP3A4 inducers and inhibitors are prohibited.

	and CYP2C9. Such concomitant medication should be avoided, if possible.”		
4.4.1 (Permitted Concomitant Therapies), 4.4.2 (Concomitant Therapies Not Permitted)	Stated that therapeutic anti-coagulation with agents such as warfarin or heparin are allowed.	Revises this to indicate that only prophylactic treatment with such agents is permitted.	Changed to be consistent with eligibility criteria (3.2.29).
4.8.1 (Mandatory Withdrawal Criteria)	“Pregnancy” and “investigator conclusion that continuation of the trial would be harmful” listed as possible withdrawal criteria.	Changes “pregnancy” and “investigator conclusion that continuation of the trial would be harmful” to events requiring mandatory withdrawal. Clarifies that pregnancy itself is not an SAE , but that it should be reported along the timelines as an SAE.	Added at the recommendation of Bayer Healthcare.
Table 7 (Study Visit Parameters)	Footnote “b” mentioned therapeutic doses of anti-coagulants.	Removes reference to this.	Therapeutic doses of anticoagulants are not permitted.
Table 7 (Study Visit Parameters)	AE/tolerability reporting required on day 1 of each cycle.	Changed to require AE reporting weekly over the phone during cycle 1 (and then day 1 of each cycle thereafter).	Added at the recommendation of Bayer Healthcare.
Table 7 (Study Visit Parameters)	n/a	Adds “& pill diary collection” to be done at the time of dispensation of study medication.	Administrative
8.1 (Supply and Storage Guidelines), 8.2 (Dose and Administration)	n/a	Removes language about the contents of regorafenib tablets.	Removed at the request of Bayer Healthcare.
10.4 (Subject Registration Procedures)	Contained some outdated language and instructions.	Updates the language and instructions pertaining to registration of study patients.	Administrative update
Appendix I	Contained some outdated language and generic instructions.	Updates the language to provide study-specific instructions and timelines for submission of study data via eCRFs.	Administrative update
Appendix IV	n/a	Adds more study-specific detail regarding how the study will be monitored.	Administrative

Appendix VI	n/a	Adds a Protocol History of Changes to summarize changes by amendment.	Administrative
Amendment 2 – September 19, 2014 Approved by SRC – November 5, 2014			
Section(s) Affected	Prior Version	Amendment 2 Changes	Rationale
List of Abbreviations, 3.1.9.6, and 2 nd NOTE in 2.1.9	PTT	PT/INR replaces PTT.	Revised for accuracy.
5.0 (Study parameters table)	Rows entitled “CT C/A/P” and “Other scans”	Combined to form one row entitled “Disease Measurements”	Clarification of disease measurement procedures
5.0 (Study parameters table)	Footnote “d” relating to “CT C/A/P” and footnote “e” relating to “Other scans”	Footnotes “d” and “e” combined into footnote “d” now relating to “Disease Measurements”. Footnote “d” revised to add “MRI and visual measurements” as options for other imaging studies that are clinically indicated. All remaining footnotes re-lettered to reflect change.	Clarification of disease measurement procedures
5.0 (Study parameters table)	Footnote “j” reading “Screening assessments must be completed within 2 weeks prior to registration, unless otherwise specified.”	Revised to add “Screening assessments may be used for C1D1 assessments if completed ≤ 2 weeks before study drug initiation.”	Revised so that patients do not repeat screening assessments unnecessarily.
5.0 (Study parameters table)	n/a	Footnote “k” added, “Adverse Event Self-Report Survey (AESRS) should be disseminated to each patient on day 1 of cycle 1, but no data is collected.”	Clarification
5.0 (Study parameters table)	n/a	Footnote “l” added. “Unless otherwise noted, on-therapy windows for testing will be as follows: imaging scans should be completed within +/- 1 week of the target time point, and labs and	Revised to add windows for on therapy testing.

		physical examination within +/- 3 days of the target time point.”	
Amendment 3 – May 18, 2015 Approved by SRC – May 20, 2015			
Section(s) Affected	Prior Version	Amendment 3 Changes	Rationale
Cover Page	IND #: TBD	Added IND exemption 120139 EXEMPT.	New information
3.1 (Inclusion Criteria)	n/a	Adds how prior therapies are counted is at the discretion of the treating physician and principal investigator.	Clarification
5.0 (Study parameters table)	Urinalysis	Changes urinalysis to urine protein/creatinine ratio (UPC) as this is what is required for eligibility in section 3.1.	Clarification
Amendment 4 – February 28, 2017			
Section(s) Affected	Prior Version	Amendment 4 Changes	Rationale
Protocol title page and Study summary	Mayo Clinic (Scottsdale), University of Wisconsin and Minnesota included as affiliate sites	Removed Mayo Clinic (Scottsdale), University of Wisconsin and Minnesota as affiliate sites. Added University of Iowa to the summary section	They are no longer affiliate sites for this study Correction of error
Section 3.1.9 Inclusion criteria	List of laboratory requirements to be considered for eligibility with a note that blood transfusion will not be allowed in order to meet criteria	Note modified to state that “subjects may not have had a transfusion within 7 days of screening assessment” for these laboratory tests.	For clarity and flexibility
Section 3.2.5 Exclusion criteria	Statement of exclusionary criteria for patients with thrombotic, embolic, venous or arterial events.	Note added to state an exception, that “ Subjects with recent DVT who have been treated with therapeutic anticoagulating agents for at least 6 weeks prior to study treatment are eligible”	For clarity and flexibility

Section 3.2.32 New exclusion criteria added
	
N/A
	
Criteria explaining the exclusion of patients that are unable or unwilling to discontinue use of strong inducers and inhibitors of CYP450
	
For added clarity, flexibility and safety

Section 4.4.1 Permitted Concomitant Therapies
	
Details about possible palliative radiation therapy during study treatment.
	
Added language: “Protocol treatment should be held 7 days before, during and 7 days after palliative radiation, or at the discretion of the site radiation oncologist. Palliative radiation cannot include target lesions.” “Palliative surgery: Protocol treatment should be held 7 days before and until the wound is healed. If treatment is not resumed within 3 weeks, the case will be reviewed by QAM and PI to determine whether or not subject can restart treatment. Palliative surgery cannot include surgery on target lesions.”
	
For added clarity, flexibility and safety

Section 5.0 study procedures table
	
Previous list of footnotes
	
Numbering of footnotes corrected and some new footnotes added: Footnote k: “Unless otherwise noted, on-therapy windows for testing will be as follows: imaging scans should be completed within +/- 1 week of the target time point, and labs and physical examination within +/- 3
	
For added clarity, flexibility and safety

		
days of the target time point “.
 
Footnote L: “Subjects will be instructed to follow-up weekly with the study team IF they are experiencing any side effects.”
 
Footnote m: “Day 1 of each cycle should be every 28 days. In the event that this day falls on a holiday or other such event, study team should use +/- 3 day window to complete pre-treatment procedures, and dispense protocol agents to patients with instructions to commence treatment on day 1. Any missed doses will not be made up and should be skipped to maintain a 28-day cycle.”
 
In addition,
 
Footnote f regarding assessments :CT C/A/P has been modified to read “ clinically indicated scans”
 
Footnote C regarding CT scans: has been modified to state: “Imaging should be done as clinically indicated (i.e. CT, MRI and visual measurements), which satisfy RECIST v 1.1 to evaluate disease (such as in extremity, head and neck). Imaging studies will be done at
	
--	--	--	--

		baseline (within 4 weeks before the first dose) and repeated after every 2 cycles of treatment (prior to each odd cycle) for tumour response evaluation.”	
Section 7.3.4 Expedited Reporting of SAEs	Previous NU protocol template language	Updated to current NU protocol template language	To align with current NUIT protocol template and IRB requirements.
Section 10.4 Subject registration procedures	Previous NU protocol template language	Updated to current NU protocol template language	To align with current NUIT protocol template and IRB requirements.
Section 10.5 Data submission guidelines (new section added)	N/A	Language added from current NU protocol template directing users to refer to the ‘stand-alone’ document in NOTIS that contains the data submission guidelines. (Previously, an outdated version of these guidelines were included in the Appendix. These have been removed in this amendment)	To align with current NUIT protocol template and IRB requirements
Section 10.6 Data management and monitoring/auditing	Reference to data Safety Monitoring plan in the Appendix.	Updated to refer to Data Safety Monitoring plan in NOTIS.	To align with current NUIT protocol template and IRB requirements
Section 10.7.2 Other protocol deviations	Sub-section Promptly Reportable Non-Compliance(PRNC)	Term replaced with Reportable New Information(RNI)	To align with current NUIT protocol template and IRB requirements
Section 10.10 Publication policy	Previous language stating conditions mandated by Bayer Healthcare	Added language from current NU protocol template	To align with current NUIT protocol template and IRB requirements
Appendix II	Entire pill dairy included in this appendix	Pill dairy removed. Language inserted asking users to refer to NOTIS for pill dairy	For convenience and to align with current NUIT protocol template
Appendix III Blood pressure log	Previous template	Updated with more details.	For convenience and clarity
Adverse Event Self-Report Survey(AESRS)	Entire survey was inserted in the appendix	Survey removed. Language inserted stating that the survey is available as a stand-	For convenience and to align with current NUIT protocol template

		alone document in NOTIS.	
Amendment 5-March 6th , 2018			
Section(s) Affected	Prior Version	Changes	Rationale
Title page and Synopsis	Study information along with affiliate site PI information	Added new affiliate site with PI information: [name] Sarcoma Oncology Research Center, CA	On-boarding of new affiliate site
Section 5.0	Baseline did not have a definite window stated	Added a -28 day baseline window.	For convenience and consistency
Section 5.0 footnote c	The language pertaining to imaging was clubbed together with chemistry laboratory tests, due to a formatting error	The imaging language has now been shifted back to footnote d and all other footnotes readjusted to its previous accurate and corresponding positions in the table.	Correction of error.
Section 5.0 footnote j	The Screening assessments had a 2 week window	The screening assessment window has been changed to 15 days	For convenience
Section 5.0	Follow-up footnotes were not clearly marked	Follow-up footnotes: (i) and (m) clearly allocated in the table	For increased clarity
Section 11 Data Submission	Data submission guidelines for Phase II study	Inserted a window of 10 days for Phase II data , as per CTO policy	To align with NU CTO policy

Amendment 6 dated 4.3.19

Section(s) Affected	Prior Version	Changes in Amend 6	Rationale
Section 3.1.7 Inclusion criteria	Progressive disease under last palliative therapy with a history of prior ifosfamide, doxorubicin or taxane therapy for angiosarcoma. Up to 4 prior therapies are allowed	Added language to state: "If patient refuses or if IV chemotherapy is contraindicated, patients will be eligible if they fail one systemic therapy."	For flexibility and clarity
